6.2.2 Roll-In Subjects

Sites will enroll a minimum of 2 and a maximum of 3 Roll-In subjects. Roll-In subjects will not be randomized to a treatment arm, but will undergo TAVI with the TriGUARD 3 CEPD and will undergo all protocol-specified follow-ups. These cases will be proctored by a Sponsor representative.

For the purposes of analysis, a subject is considered enrolled in the Roll-In phase of the study when:

- The patient has been judged to meet all inclusion and no exclusion criteria (including approval by the PRC), and has signed a Patient Informed Consent form
- The TriGuard HDH or TriGUARD 3 device has been introduced into the patient's bloodstream

6.2.3 Withdrawal and Replacement of Patients

Subjects can withdraw from the study at any time; the reason(s) for withdrawal (if given) will be documented. All data available at the time of withdrawal (if any) will be used for analysis. There will be no further follow-up (per this study protocol) on a subject who has withdrawn. Subjects who withdraw from the study will not be replaced. The withdrawal of a subject can be initiated by the Investigator if he/she determines it is in the best interest of the patient.

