6.2 Subject Enrollment

6.2.1 Screening and Enrollment

Patients meeting indications for TAVI will be pre-screened for study eligibility by a member of the research team, including a review of the patient's medical history and any existing diagnostic imaging testing that has been performed as a part of the patient's normal medical care.

Based on the results of pre-screening, potentially eligible patients will be asked to provide written informed consent. Informed consent must be documented prior to the performance of any study-specific screening procedures or assessments. Following receipt of informed consent, a baseline screening assessment will be conducted to verify eligibility; the required documentation must also be provided to the Patient Review Committee (§11.1) to determine anatomic eligibility for the trial.

The patient will be considered enrolled in the study when all the following criteria have been met:

- The patient has provided written informed consent
- Baseline screening has been conducted and:
 - The Patient Review Committee has determined that the patient meets the evaluated anatomic eligibility criteria (based on imaging analysis by independent CT core laboratory) AND
 - The investigator has determined that the patient meets all applicable remaining inclusion and no exclusion criteria
- The point of enrollment has been reached:
 - **For evaluable subjects** (Intervention and Control groups), the point of enrollment is the moment of randomization. Randomization will occur:
 - Within 72 hours prior to the scheduled initiation of the TAVI procedure AND
 - After the investigator has confirmed the subject meets all anatomic eligibility criteria
 - **For Roll-In subjects**, the point of enrollment is the introduction of the TriGuard HDH or TriGUARD 3 device into the bloodstream.

A screening log will be completed to document the enrollment and subject number, or reason for non-enrollment of subjects screened but not enrolled in the study. All enrolled subjects are required to complete all assigned follow-up assessments. No single site was permitted to enroll more than 20% of the total number of evaluable subjects (i.e., no single site may enroll more than 57 evaluable subjects in the initial randomized cohort [in addition to any roll-in subjects] in Phase I, and no more than 45 randomized subjects in the initial randomized cohort [in addition to any roll-in subjects] in Phase II).

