6.3 Blinding

This is a single-blind study. The following individuals will be blinded to the subject's treatment allocation:

- Subject and his/her family members
- Site personnel administering neurological evaluations (NIHSS and mRS); these individuals will also be blinded to DW-MRI results
- Members of the Data Safety Monitoring Committee
- MRI Core Laboratory personnel performing imaging analysis

Un-blinding will occur only after the database has been locked for the analysis of the primary endpoint or to protect subject rights, welfare, or well-being at the request of the DSMB. The circumstances under which the DSMB may request unblinding to treatment allocation will be outlined in the DSMB charter prior to the onset of the trial.

If a site investigator determines it is necessary to reveal treatment allocation to the subject as a result of complication or injury, he or she is requested to notify the Sponsor.

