7.4 TAVI Procedure

TAVI will be performed according to standard institutional practice under local or general anesthesia and via the transfemoral approach at the discretion of the investigator.

In subjects in the Intervention or Roll-in Groups, the TriGuard HDH or TriGUARD 3 device will be advanced and deployed across the aortic arch to cover the ostia of the 3 major vessel takeoffs (innominate, left carotid and subclavian arteries) at the initiation of the TAVI procedure and withdrawn at the completion of the procedure. Please refer to the TriGuard HDH or TriGUARD 3 Instructions For Use for additional information.

Device coverage and positioning must be verified by fluoroscopy (a steep left anterior oblique [LAO] view is recommended), with particular attention paid to 1.) Device coverage after initial deployment, 2.) Device positioning after final deployment of the first prosthetic valve, and 3.) Device positioning after the procedure is complete (i.e., after any additional post-dilatation or additional valve implantations have been completed, and the TAVR delivery system has been removed). All imaging should be forwarded to the Angiographic Core Laboratory for analysis. For additional details, please refer to the Angiographic Imaging Acquisition Guidelines (§16.8).

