15.8 Termination of the Study

Keystone Heart Ltd. reserves the right to terminate the study but intends only to exercise this right for valid scientific or administrative reasons and reasons related to protection of patients. Possible reasons for early trial termination include:

- Unanticipated Adverse Device Effects (UADEs) present an unreasonable risk to patients
- Recommendation from the DSMB

If the trial is terminated early, the Sponsor will provide a written statement to the Investigators to enable notification of the IRBs/ECs. The Sponsor will also inform the FDA and the relevant Competent Authority (where required). In the case of early termination of trial enrollment, follow-up visits will continue for all enrolled subjects.

The Sponsor may terminate an investigator's or site's participation in the study if there is evidence of an investigator's failure to maintain adequate clinical standards or evidence of an investigator or staff's failure to comply with the protocol. Should investigator or site

participation be considered for termination, the Sponsor (or designee) will ensure appropriate follow-up for any subjects enrolled, including transferal to the supervision of an approved investigator and approval of transfer of subject oversight and follow-up by the appropriate IRB/EC. Notification of study site suspension or termination will occur no later than five (5) working days after the Sponsor makes the determination. A suspended or terminated study site may not be reinitiated without approval of the reviewing IRB/EC. The investigator should notify the IRB/EC in writing as soon as possible but no later than within 10 days if the premature termination is related to safety or compliance issues. The same procedure will be applied to the Competent Authority where required.

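### Section 6.2.3 has one withdrawal category that ends all follow-up, even when the investigator starts it, so later death and stroke status is lost for Tier 1 and the 7-day endpoints

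*Combined protocol and SAP*

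**What the plan says.** Section 6.2.3 (Withdrawal and Replacement of Patients) recognises one kind of withdrawal. Subjects may leave at any time, and the investigator may also act: "The withdrawal of a subject can be initiated by the Investigator if he/she determines it is in the best interest of the patient". The consequence is the same in both cases: "There will be no further follow-up (per this study protocol) on a subject who has withdrawn". What was collected earlier is kept ("All data available at the time of withdrawal (if any) will be used for analysis"), and withdrawn subjects are not replaced. Section 14.2 asks the site to file the reason and the subject's status at withdrawal, but nothing later.

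Other provisions bear on this rule:

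- Section 6.2.1 sets the general expectation: "All enrolled subjects are required to complete all assigned follow-up assessments". It places randomization as follows: "Within 72 hours prior to the scheduled initiation of the TAVI procedure".
- Section 6.3 (and the synopsis) lists who is blinded: the subject and family, the site staff doing the neurological scales, the data monitoring board and the MRI core laboratory. The treating investigator is not listed.
- Section 7.4 has the device deployed "at the initiation of the TAVI procedure and withdrawn at the completion of the procedure".
- Section 7.7.2 obtains death and stroke at 90 days by telephone, and asks for source documents so that the clinical events committee can adjudicate.
- Section 12.4.2 limits the safety analysis to subjects with an event or at least 23 days of follow-up. A tipping-point analysis covers those who withdrew earlier without an event.
- Section 12.4.3 states a missing-data method for DW-MRI lesion volume only.

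**The concern.** Death or stroke to 30 days is Tier 1 of the primary efficacy hierarchy. Two of the five tested secondary endpoints (all stroke, and death or stroke) are read at 7 days. Both events are also components of the primary safety composite, and section 12.2.1.1.1 requires both primary endpoints to succeed.

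For a withdrawal after the procedure there is no study treatment to stop. Excusing a patient from visits or a scan can serve that patient. Ending a record check for death and stroke does not, unless the patient has asked for it. The rule also allows someone not on the blinded list to end outcome collection for a given subject. The protocol already runs a procedure, in section 7.7.2, that could supply what is lost.

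**Working it through.** **Plan's own safety figures.** Inputs (sections 12.2.1.1.1 and 12.2.4.1): performance goal 34.4%, expected rate 25%, one-sided alpha 0.05, 179 evaluable, 85% power, critical value 28.5%, 190 after 5% loss.

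- Uncorrected one-sample z-test: n = [(1.645·√(0.344·0.656) + 1.036·√(0.25·0.75)) / 0.094]² = 171.3, so 172. With continuity correction it is 182. The stated 179 lies between.
- Power at 179 is 86.4% by the z formula and 84.0% by the exact test, in line with 85%.
- Critical value: 51/179 = 28.5%. Inflation: 179/0.95 = 188.4, so 189, against 190 stated.

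The stated figures reproduce. The point rests on the withdrawal rule, not on an arithmetic error.

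**Tier 1.** Inputs (section 12.2.4.1.2): 150 device and 75 new control subjects, Tier 1 rates 6% and 11%, non-MRI loss 5%.

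- Expected events: 0.06 × 150 = 9.0 and 0.11 × 75 = 8.25, about 17 in all.
- Unknown if the whole 5% is withdrawal: 7.5 + 3.75 = 11.25, about 11 of 225.
- Suppose the stated rates hold among those observed and a fraction u of each arm is unknown. An arm with observed rate p then lies between (1 − u)p and (1 − u)p + u.
- At u = 0.05 the device arm runs from 5.7% to 10.7%, and the control arm from 10.45% to 15.45%.
- Control minus device therefore lies between 0.05(1 − u) − u and 0.05(1 − u) + u.

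| Withdrawal share of the 5% loss | Worst case for device (device vs control) | Best case for device (device vs control) |
|---|---|---|
| All (u = 0.05) | 10.7% vs 10.5% | 5.7% vs 15.5% |
| Half (u = 0.025) | 8.4% vs 10.7% | 5.9% vs 13.2% |
| None | 6% vs 11% | 6% vs 11% |

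At the upper limit the assumed 5-point difference can vanish or nearly double.

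**Safety.** The largest possible number unknown is 190 − 179 = 11. If the 11 are added back, the denominator is 190 and the limit moves too: 0.344 − 1.645·√(0.344·0.656/190) = 28.7%, which is 54 events.

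- At the pass limit of 51/179, 4 of the 11 counted as events give 55 and overturn success.
- At 45/179 (25%), 10 of the 11 are needed.
- If the decision uses the normal-approximation upper confidence bound, the limit is 55, and 5 and all 11 are needed.

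Knowing the outcome of all 190 would raise power only from 86.4% to 88.3%.

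**The case against.** Much of the strongest reply stands.

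- **Existing handling.** Events before withdrawal are used. Safety subjects followed to day 23 stay in, and a tipping-point analysis addresses the rest. The 5% loss is already in the power calculations. This limits the damage but recovers no outcomes.
- **Declining the MRI.** A reader might infer that refusing the scan ends follow-up. It does not: section 12.2.4.1.2 counts non-compliance with the scan as MRI loss (15%), separate from the 5%.
- **Size.** A reader might take the 5% as withdrawals. The documents do not give that share. For safety, the 5% expressly includes subjects outside the As Treated set. Some losses will be subjects who cannot be reached, whom no redrafting recovers.
- **Safety margin.** Comparing 45 expected events with the limit of 51 suggests that 6 unknown events exhaust the margin. That mixes denominators, because with 190 subjects the limit is 54.
- **Selective withdrawal.** The text confines investigator withdrawal to the patient's best interest, and nothing shows that it would be used by arm. That the investigator knows the allocation is inferred from the blinded list and from placing the device. It is not stated.
- **Section 15.8.** It says "In the case of early termination of trial enrollment, follow-up visits will continue for all enrolled subjects". That concerns subjects who have not withdrawn, so it does not contradict section 6.2.3.
- **Period before TAVI.** Up to 72 hours can separate randomization and TAVI. A withdrawal then does forestall treatment.
- **Text not at hand.** Section 12.1 defers some endpoint detail to the SAP, and consent pages are not in the text. A Tier 1 missing-data rule or partial-consent wording may exist there.

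A further objection concerns the remedy: a call about death and stroke cannot show that a subject is free of the other five safety components. This is correct, and the fix below is narrowed for it.

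**Conclusion.** The point holds in limited form. Section 6.2.3 states a rule rather than leaving a gap: any withdrawal, including one started by an investigator not on the blinded list, ends protocol follow-up. Followed as written, it loses later death and stroke status for Tier 1 and the 7-day secondary endpoints.

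The figures above are limits, not forecasts. They assume that the whole 5% loss is withdrawal, that the planned rates hold among those observed, and that the unknowns fall at one extreme or the other. They also use the 75 new controls only, without the 63 from Phase I. They shrink as the withdrawal share falls.

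For safety the exposure is smaller. A result at the planned rate would survive unless nearly all of the unknowns were events, while a result at the pass limit would be fragile. The benefit of a change lies in the validity of the comparison, not in power. The documents do not support reading this as evidence of biased withdrawal or as a conflict between sections.

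**What to change.** Rewrite section 6.2.3 as follows:

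1. The investigator may stop study-specific procedures but may not end outcome follow-up.
2. Only the subject may withdraw consent to follow-up, and the form records how far that withdrawal extends.
3. For every other subject, obtain 30-day and 90-day death and stroke status by the telephone and source-record route of section 7.7.2, with adjudication by the clinical events committee. Use it in Tier 1 and the 7-day endpoints.
4. For the safety composite, count a subject as event-free only if records cover all seven components to at least day 23. Otherwise keep the subject in the tipping-point analysis. Without this, the inclusion rule of section 12.4.2 would admit events learned by telephone while event-free subjects stayed out, which would bias the rate upward.
5. Unless the SAP already does so, state how a subject with unknown Tier 1 status is scored, and add a sensitivity analysis.

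The cost is one protocol paragraph, a consent-form line, a CRF field and a few extra calls or record requests. The subject's right to leave entirely is unchanged.

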6.2.4 Protocol Deviations

All deviations from the requirements of this Clinical Investigation Plan will be considered protocol deviations.

A major protocol deviation is a protocol deviation that may affect the scientific soundness of the protocol or the rights, safety, or welfare of the patients. Major protocol deviations require urgent reporting to the Study Monitor and the Institutional Review Board/ Ethics Committee.

Patient-level deviations are those that occur in direct association with a specific study patient. These include, but are not limited to, deviations from informed consent procedures, inclusion/exclusion criteria, protocol-specified procedures and assessments, and device handling and usage.

Site-level deviations are those that occur at the study center but are not directly related to a study specific patient. All efforts should be made to avoid any protocol deviation.

6.3 Blinding

This is a single-blind study. The following individuals will be blinded to the subject's treatment allocation:

- Subject and his/her family members
- Site personnel administering neurological evaluations (NIHSS and mRS); these individuals will also be blinded to DW-MRI results
- Members of the Data Safety Monitoring Committee
- MRI Core Laboratory personnel performing imaging analysis

Un-blinding will occur only after the database has been locked for the analysis of the primary endpoint or to protect subject rights, welfare, or well-being at the request of the DSMB. The circumstances under which the DSMB may request unblinding to treatment allocation will be outlined in the DSMB charter prior to the onset of the trial.

If a site investigator determines it is necessary to reveal treatment allocation to the subject as a result of complication or injury, he or she is requested to notify the Sponsor.

7.0 Study Procedures

7.1 Study Schedule of Procedures and Assessments

Table 7. Study Schedule of Procedures and Assessments- Phase I (TriGuard HDH)

	Screening/ Baseline	Procedure (day 0)	Post-Procedure / Pre-Discharge	30-day Follow-up (30 ± 7 days)	90-day Follow-up (90 ± 14 days)
Written Informed Consent	X				
Medical History	X				
Physical Examination ¹	X		X	X	X
Review of Eligibility Criteria ²	X	X			
Clinical Frailty Scale	X				X
12-lead ECG ³	X		X		
Concomitant Medications	X	X	X	X	X
Pregnancy Test ⁴	X				
Hematology/Chemistry ⁵	X		X		
Cardiac Enzymes ⁶	X		X		
CT Imaging ⁷	X				
Cerebral DW-MRI ⁸			X		
NIH Stroke Scale ⁹	X		X	X	X
Modified Rankin Scale ⁹	X		X	X	X
Neuropsychological test battery ¹⁰	X		X	X	X
SF-36 Health Survey ¹¹	X			X	X
TAVI		X			
Echocardiography (SOC) ¹²			X		
TriGuard HDH deployment		X			
Adverse Events		X	X	X	X

¹ Physical examination to include heart rate, blood pressure, and ischemic / anginal status (CCS or silent ischemia). The screening/baseline assessment must also include NYHA functional capacity, height, and weight.

² If the full screening/baseline review of eligibility criteria is conducted before the day of enrollment, the following repeat review of selected eligibility criteria should be performed on the day of enrollment and randomization (§6.2.1) to confirm study eligibility, using the most recent available laboratory values and clinical assessments: 1.) Ensure that the subject has not had symptoms or chemistry results indicating acute myocardial infarction (§6.1.2.1.5); 2.) Ensure that the most recent eGFR remains ≥30 (§6.1.2.1.10); 3.) Ensure that there are no signs of cardiogenic shock or severe hypotension (systolic blood pressure <90 mm Hg) (§6.1.2.1.13); and 4.) Review the planned approach for TAVI, as certain approaches will make the subject ineligible for the study (§6.1.2.1.1, §6.1.2.1.2)

³ Screening/baseline ECG may be performed up to 30 days prior to procedure, as long as there have been no intervening signs or symptoms of myocardial ischemia (in which case the ECG should be performed within 24 hours prior to enrollment). The post-procedure ECG must be performed within 24 hours of the procedure or prior to hospital discharge (whichever occurs first).

⁴ Female patients of childbearing potential must have a pregnancy test within 14 days prior to the procedure

⁵ Hematology and chemistry within 14 days prior to the procedure are defined in §7.2.

⁶ For the screening/baseline assessment, cardiac enzymes (CK), isoenzymes CK-MB or troponins obtained up to 14 days prior to the procedure (or on current admission) are acceptable, provided there has been no intervening episode of myocardial ischemia (in which case cardiac enzymes should be confirmed within 24 hours prior to enrollment). Post-procedure, CK/CKMB or troponin (preferably CKMB isoenzyme) will be measured at 12-24 hours post-procedure, at 24±3 hours after the first measurement, and again at 72±6 hours post-procedure or at discharge (whichever occurs first). If cardiac biomarkers are elevated, they should be repeated daily until values show a decline.

- ⁷ Multi-slice CT angiography of the left heart, aorta, great vessels and peripheral access vessels performed up to 1 year prior to procedure should be submitted for review.
- ⁸ DW-MRI must be performed 2 to 5 days (≥ 48 to < 144 hours) post-procedure.
- ⁹ The NIHSS and mRS (in addition to the neuropsychological test battery) must be performed 2 to 5 days (≥ 48 to < 144 hours) post-procedure by a neurologist or a clinical designee (e.g. neurology fellow). A full neurological evaluation should be performed by a neurologist in all patients in whom a stroke or TIA is suspected on the basis of the NIHSS, mRS, or other signs or symptoms.
- ¹⁰ A brief paper-and-pencil neuropsychological test battery (§16.7), will be administered up to 30 days prior to procedure, 2 to 5 days (≥ 48 to < 144 hours) post-procedure, and at the 30- and 90-day clinic visits.
- ¹¹ The Short Form 36 Health Survey (SF-36) (§16.11) will be administered up to 30 days prior to procedure and at the 30- and 90-day clinic visits. When administered during a visit that includes other assessments, the SF-36 should be performed first.
- ¹² If echocardiography (transthoracic or transesophageal) was performed after TAVR prosthesis implantation as part of the standard of care, the relevant parameters (including mean aortic valve gradient, peak velocity, and degree of prosthetic aortic valve regurgitation) must be captured on the eCRF for evaluation in-hospital TAVI device success (§□).

Table 7a. Study Schedule of Procedures and Assessments- Phase II (TriGUARD 3)

	Screening/ Baseline	Procedure (day 0)	Post- Procedure	30-day Follow-up (30 \pm 7 days)	90-day Follow-up (90 \pm 14 days)
Written Informed Consent	X				
Medical History	X				
Physical Examination ¹	X		X	X	
Review of Eligibility Criteria ²	X	X			
Clinical Frailty Scale	X				
12-lead ECG ³	X		X		
Concomitant Medications	X	X	X	X	
Pregnancy Test ⁴	X				
Hematology/Chemistry ⁵	X		X		
Cardiac Enzymes ⁶	X ⁶		X ⁶		
CT Imaging ⁷	X				
Cerebral DW-MRI ⁸			X		
NIH Stroke Scale ⁹	X		X	X	
Modified Rankin Scale ⁹	X		X	X	
TAVI		X			
Echocardiography (SOC) ¹⁰			X		
Device deployment		X			
Adverse Events		X	X	X	
Phone call to assess mortality/ Stroke					X

¹ Physical examination to include heart rate, blood pressure, and ischemic/anginal status (CCS or silent ischemia). The screening/baseline assessment must also include NYHA functional capacity, height, and weight.

² If the full screening/baseline review of eligibility criteria is conducted before the day of enrollment, the following repeat review of selected eligibility criteria should be performed on the day of enrollment and randomization (§6.2.1) to confirm study eligibility, using the most recent available laboratory values and clinical assessments: 1) Ensure that the subject has not had symptoms or chemistry results indicating acute myocardial infarction (§6.1.2.1.5); 2) Ensure that the most recent eGFR remains ≥ 30 (§6.1.2.1.10); 3) Ensure that there are no signs of cardiogenic shock (§6.1.2.1.13); and 4) Review the planned approach for TAVI, as certain approaches will make the subject ineligible for the study (§6.1.2.1.1).

³ Screening/baseline ECG may be performed up to 30 days prior to procedure, as long as there have been no intervening signs or symptoms of myocardial ischemia (in which case the ECG should be performed within 24 hours prior to enrollment). The post-procedure ECG must be performed within 24 hours of the procedure or prior to hospital discharge (whichever occurs first).

⁴ Female patients of childbearing potential must have a pregnancy test within 14 days prior to the procedure

⁵ Hematology and chemistry within 14 days prior to the procedure are defined in §7.2.

⁶ For the screening/baseline assessment, cardiac enzymes (CK), isoenzymes CK-MB or troponins obtained up to 14 days prior to the procedure (or on current admission) are acceptable, provided there has been no intervening episode of myocardial ischemia (in which case cardiac enzymes should be confirmed within 24 hours prior to enrollment). Post-procedure CK/CKMB or troponin (preferably CKMB isoenzyme) will be measured post procedure when clinically indicated. If cardiac biomarkers are elevated, they should be repeated per local standard of care.

⁷ Multi-slice CT angiography of the left heart, aorta, great vessels and peripheral access vessels performed up to 1 year prior to procedure should be submitted for review.

⁸ DW-MRI must be performed 2 to 5 days (≥ 48 to < 144 hours) post-procedure.

⁹ The NIHSS and mRS must be performed 2 to 5 days (≥ 48 to < 144 hours) post-procedure by a neurologist or a clinical designee (e.g. neurology fellow). A full neurological evaluation should be performed by a neurologist in all patients in whom a stroke or TIA is suspected on the basis of the NIHSS, mRS, or other signs or symptoms.

¹⁰ If echocardiography (transthoracic or transesophageal) was performed after TAVI prosthesis implantation as part of the standard of care, the relevant parameters (including mean aortic valve gradient, peak velocity, and degree of prosthetic aortic valve regurgitation) must be captured on the eCRF for evaluation in-hospital TAVI device success.

